# 11.2.3 Biomarker endpoint analyses

For continuous data, summary statistics including n, mean, standard deviation, median, minimum and maximum or IQR will be computed. Prostatic T cell infiltration pre-and-post biopsy will be described and graphed over time. Differences in either time point compared to baseline will be compared with a t-test or non-parametric alternative. Cox models will be implemented to explore the relationship of treatment combination, prostatic T cell infiltration, and progression-free survival.

# 11.2.4 Interim analyses

Toxicity will be monitored in all patients who receive at least one dose of durvalumab + tremelimumab, even if the patient is not evaluable for the efficacy or biomarker endpoints. Based on the method of Thall et al. (1995) continual monitoring after the 6th patient is planned. Calculations were performed in Multc Lean 2.1.

Denote the probability of TOX by  $\Theta$  E. We assume  $\Theta$  E  $\sim$  beta (0.8, 1.2). Our stopping rule is given by the following probability statement: Pr( $\Theta$  E > 0.40 | data) >0.90. That is, we will stop

if, at any time during the study, we determine that there is more than a 90% chance that the extreme toxicity rate is more than 40%, a constant rate that is the maximum acceptable for TOX. The stopping boundaries for this toxicity rule are to terminate if the number of TOX events compared to the number of patients who have received at least one dose of treatment exceeds the limits in this table. Continual monitoring will be carried out monthly after the 6th patient is treated according to the following table:

Table 4. Toxicity monitoring rules (after the 6 patient is treated)

If there are this many patients with TOX:	5	6	7	8	9	10	11	12	13	14
Stop if there are this many or fewer patients treated with ≥1 dose of study drug:	7	9	11	13	15	17	20	22	24	26

If the trial enrolls 27 patients, the trial will stop there regardless of the number of patients with TOX. However, the trial may stop between 20 and 27 patients once 20 evaluable patients are enrolled unless the trial stops for toxicity first. This means the probability of stopping early is overestimated in the operating characteristics below since the trial may stop for evaluability after 24 patients are enrolled. In this case, the probability of stopping for TOX is overestimated by the probability of stopping at 25 or 26 patients. Similarly, the median, 25th, and 75th percentile of the sample sizes may be slightly overestimated.

Table 5. Operating Characteristics for the Toxicity Monitoring Rule assuming all 27 patients are enrolled

True TOX rate	Probability of Stopping Early	Probability of Enrolling ≥ 20 Patients	Average Number of Patients	Average Number of Patients with TOX	Median (25 th %ile, 75 th %ile)
25	0.02	0.98	26.6	6.6	27 (27, 27)
30	0.06	0.95	26.0	7.8	27 (27, 27)
35	0.13	0.89	25.0	8.7	27 (27, 27)
40	0.25	0.80	23.3	9.3	27 (27, 27)
45	0.41	0.67	21.0	9.5	27 (13, 27)
50	0.59	0.53	18.3	9.2	20 (11, 27)
55	0.75	0.47	15.5	8.5	13 (7, 26)

MDACC Investigational New Drug (IND) office will review Efficacy/Toxicity data with Principal Investigator (and statistician if needed) at a predetermined interval as indicated next: The first analysis will occur after the first 6 subjects are treated for at least 2 cycles, and reports submission will continue in cohort size of 2 subjects, thereafter. On every report submission, the information from previous reported patients will need to be updated.

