# 11.2 Methods of statistical analyses

# 11.2.1 Primary safety analyses

For the interim safety monitoring described below, an extreme toxicity (TOX) will be defined as any grade 3 or higher adverse event that is possibly, probably, or definitely related to any therapy received on this protocol and occurs within the first 8 weeks of therapy (2 cycles) with one exception. Any grade 3 or higher adverse event that is potentially treatable with steroids will only count as an extreme toxicity if it does not improve to grade 1 or better within 2 weeks of steroid therapy.

At the end of the trial, all adverse events will be tabulated by their CTCAE v4.03 name, counted once at the worst grade and the ultimate attribution within the patient. Exploration of these measures by cycle may also be presented.

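### Table 5's stopping probabilities assume immediate 8-week outcomes and a look after every patient; neither written look schedule works that way, and patients still in the window count as TOX-free

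*Combined protocol and SAP*

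**What the plan says.** Section 11.2.1 defines TOX as a related grade 3 or higher event in the first 8 weeks (2 cycles). An event potentially treatable with steroids counts only "if it does not improve to grade 1 or better within 2 weeks of steroid therapy", so some events take up to 2 further weeks to classify.

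Section 11.2.4 puts a beta(0.8, 1.2) prior on the TOX probability and stops if Pr(rate > 0.40 | data) > 0.90. The instruction is to "terminate if the number of TOX events compared to the number of patients who have received at least one dose of treatment" exceeds Table 4. On timing it says two things:

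- "Continual monitoring will be carried out monthly after the 6th patient is treated".
- In the paragraph on the IND Office review: "The first analysis will occur after the first 6 subjects are treated for at least 2 cycles". Later reviews in that paragraph come with every 2 further patients.

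Table 5 is headed as assuming that all 27 patients are enrolled, but "the trial may stop between 20 and 27 patients once 20 evaluable patients are enrolled". The only quantified caveat is for a trial that ends at 24: "the probability of stopping for TOX is overestimated by the probability of stopping at 25 or 26 patients".

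Section 11.3 cites Table 5 as showing that the numbers are enough to establish safety, and expects accrual within 6 months. No section says that enrolment waits for pending outcomes, or how a patient still in the 8-week window counts.

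**The concern.** A rule that compares events so far with everyone dosed so far treats a pending patient as a non-event. At 20 to 27 patients in 6 months, about 6 to 8 patients are pending at any time, so the rule is diluted throughout accrual. For example, 5 TOX among 7 patients with complete follow-up is a stop. Dose 6 more patients and the same 5 events sit against 13, where Table 4 requires 8.

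Safety is the only primary objective, this is the plan's only quantitative stopping rule for the combination, and Table 5 is the evidence offered that it protects patients. If the rule as written stops less often and later than Table 5 says when the true rate exceeds the plan's own 40% maximum, more patients are treated at that rate than the plan implies. Two people applying the text could also look at different times and decide differently.

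**Working it through.** **Inputs.** From Section 11.2.4: the prior, the 40% limit, the 0.90 cut-off, Table 4 and a maximum of 27. From Section 11.2.1: the 8-week window and the 2-week steroid wait. From Section 11.3: 6-month accrual, so 20/6 = 3.33 to 27/6 = 4.5 patients per month. Assumed, because the documents do not give them: TOX onset uniform over weeks 0-4, 0-8 or 4-8; a steroid wait of 0 or 14 days applied to every TOX; Poisson or evenly spaced accrual.

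**1. Table 4.** Stop at x TOX in n patients if the Beta(0.8 + x, 1.2 + n − x) tail above 0.40 exceeds 0.90. For 5/7 the tail is 0.934 (stop) and for 5/8 it is 0.875 (continue). For 11/20 it is 0.901 and for 11/21 it is 0.861. All ten limits reproduce.

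**2. Table 5.** Exact binomial recursion, each outcome known before the next patient, a look after every patient from 6 to 26:

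| True rate | 25% | 30% | 35% | 40% | 45% | 50% | 55% |
|---|---|---|---|---|---|---|---|
| Table 5 P(stop) | 0.02 | 0.06 | 0.13 | 0.25 | 0.41 | 0.59 | 0.75 |
| Recomputed | 0.023 | 0.059 | 0.131 | 0.248 | 0.407 | 0.586 | 0.753 |

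Mean enrolment at 50% is 18.3, as stated. These are therefore the assumptions behind the table.

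**3. Exact variants, no onset assumption.**

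| Setting | P(stop) 40% | P(stop) 50% | P(stop) 55% | Mean N at 50% |
|---|---|---|---|---|
| Look after each patient, to 27 | 0.248 | 0.586 | 0.753 | 18.3 |
| Complete cohorts of 2, to 27 | 0.206 | 0.549 | 0.727 | 20.0 |
| Look after each patient, ends at 20 | 0.201 | 0.475 | 0.631 | 15.2 |
| Complete cohorts of 2, ends at 20 | 0.126 | 0.353 | 0.506 | 16.6 |

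Complete cohorts of 2 require holds after patients 6, 8, ..., 18: 7 × 8 = 56 weeks to reach patient 20, before any steroid wait.

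**4. The plan's caveat.** At 50%, the probability of stopping at 25 or 26 is 0.019. If enrolment ends at 20, the overstatement is 0.586 − 0.475 = 0.111, almost six times as large.

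**5. Calendar-time simulation, no hold, Table 4 applied to all dosed patients, true rate 50%** (Table 5: 0.59). P(stop) is the probability of crossing the boundary before the 27th enrolment.

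- Monthly looks with every outcome known at once: 0.43-0.53. Look spacing alone costs this much.
- Monthly looks, Poisson accrual, no steroid wait, onset weeks 0-4 / 0-8 / 4-8: 0.38 / 0.26 / 0.17 at 3.33 per month and 0.31 / 0.18 / 0.09 at 4.5. With a 14-day wait: 0.27 / 0.16 / 0.11 and 0.17 / 0.09 / 0.04.
- Monthly looks, onset weeks 0-4 or 0-8, no wait, Poisson or even accrual: 0.14-0.39.
- Looks when the 6th, 8th, ... patient completes 8 weeks, Poisson accrual: 0.05-0.40. On average 12.1 (3.33 per month) or 14.3 (4.5 per month) patients are already dosed at the first review.
- All 48 combinations of monthly or pre-enrolment looks, onset, steroid wait and accrual: 0.01-0.51. None reaches 0.59. The lowest values need late onset plus the steroid wait.
- Slower accrual narrows the gap: 0.16-0.52 if 27 patients take 12 months and 0.38-0.56 if 24 months, over the accrual patterns and look timings tried.

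At 55% (Table 5: 0.75), monthly looks alone give 0.61-0.70. Monthly looks with onset weeks 0-4 or 0-8 and no wait give 0.24-0.56.

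**6. Mean enrolment at 50%**, monthly looks, Poisson accrual, no wait, onset 0-4 and 0-8: 22.8 and 24.5 (3.33 per month), 23.8 and 25.6 (4.5 per month), against 18.3. If enrolment ends at 20: 18.1 and 19.1, 18.7 and 19.5, against 15.2.

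**7. Two other Table 5 entries.** Under the table's own assumptions, cumulative stopping by n = 19 at 55% is 0.631, so P(enrolling at least 20) = 1 − 0.631 = 0.37, not 0.47. At 50%, cumulative stopping is 0.227 at n = 8 and 0.295 at n = 9, so the 25th percentile is 9, not 11.

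**The case against.** The two schedules may be parallel processes. Only the monthly one is tied to Table 4; the other is an IND Office review of efficacy and toxicity data. The plan also says that it will stop if the criterion is met at any time, which can make monthly a minimum frequency. This is a fair reading, but the second paragraph calls its look the first analysis, and neither process is the one that Table 5 models. Looking before every enrolment at 6-month accrual still gives at most about 0.51.

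If outcomes are complete, cohorts of 2 give 0.55 against 0.59. That stands: on that reading Table 5 is nearly right. It requires a hold that the plan does not state and that does not fit 6-month accrual.

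Ending at exactly 20 assumes no non-evaluable patients, which is unlikely at a high TOX rate, and the sentence about 25 or 26 patients can be read as an example. So the figures for 20 are a bound. The simulated range is wide because onset, steroid wait and accrual pattern are assumed, and the wait applies only to steroid-treatable events. This affects the size; the direction was the same in every scenario tested.

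Finally, this is a 27-patient pilot without formal hypotheses, and the individual discontinuation and expedited reporting rules operate regardless. At a true 25% rate the absolute change is about 0.02. All of that is true, but the pilot's primary objective is safety, and Table 5 is its stated justification.

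**Conclusion.** The concern holds. The text alone establishes that the denominator includes pending patients as TOX-free, that no hold or pending-patient rule is stated, and that two look schedules are given. Exact calculation shows that Table 5 models neither.

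The size depends on the reading. With accrual held for complete cohorts of 2, the loss at a true 50% rate is small (0.55 against 0.59, and 20.0 − 18.3 = 1.7 more patients on average), but the 6-month accrual statement then fails. Without a hold at 6-month accrual, and with onset over weeks 0-4 or 0-8 and no steroid wait, monthly looks give 0.14-0.39, and about 4 to 7 more patients are enrolled on average than Table 5 implies (about 3 to 4 if enrolment ends at 20). Late onset or a steroid wait lowers the stopping probability further; slower accrual raises it. The Table 4 limits are correct and do not change. This should be corrected before the rule is relied on.

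**What to change.** 1. Reconcile the two timing statements in Section 11.2.4 into one look schedule, and state whether accrual is held for pending outcomes. If it is, revise the 6-month accrual statement in Section 11.3.
2. If it is not held, state how pending patients count. One option: weight each TOX-free patient by the fraction of the 8-week window completed, count a TOX patient as 1, and leave a patient whose steroid response is still being judged out of both counts. The prior, the 40% limit and the 0.90 cut-off stay.
3. Recompute Table 5 for the chosen rule at the planned accrual, with stated early and late onset and steroid-wait assumptions, for enrolment ending at 20 and at 27, including false stopping at 25-40%.
4. Check the entries 0.47 (recomputed 0.37) and 11 (recomputed 9) against the source output.

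The cost is protocol wording and a short simulation, with no extra patients or visits unless a hold is chosen. The weighted option does not restore Table 5. With monthly looks at 6-month accrual, over early to late onset and a 0 or 14-day wait, it gives about 0.11-0.56 at a true 50% rate, against 0.01-0.39 for the dosed denominator on the same grid. Its false stopping is 0.00-0.05 at 25%, 0.00-0.09 at 30%, 0.01-0.16 at 35% and 0.03-0.26 at 40%, against 0.02, 0.06, 0.13 and 0.25 in Table 5. The recomputed table should therefore be expected to show lower stopping probabilities at high TOX rates than the present one.

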# 11.3 Determination of sample size

The selection of 20 evaluable patients was intended as a pilot sample size with sufficient numbers to establish safety in this population as shown in Table 5 above while providing sufficient numbers for the secondary endpoints. This will allow investigation of a few marker endpoints and establish safety and feasibility of measuring the markers of interest while being able to accrue within 6 months. No formal hypotheses are planned. These patients will form the basis of designing a hypothesis-driven study in the future. However, we can make a statement about what might be detected in secondary endpoints at this sample size. The association between CD3 change and PSA PFS will be explored with a Cox model with CD3 as a continuous measure. Assuming that

75% (80%) of patients will progress by the end of the study, 20 patients will have 80% power to detect a regression coefficient of 0.72 (0.70) at a 2-sided 5% significance level, assuming the change in CD3 has a standard deviation of 1. The regression coefficient of 0.72 (0.70) is equivalent to a hazard ratio of 2.1 (2.0) or a doubling of risk per unit increase in CD3 (Calculations performed in NCSS-PASS 2005). This would hold true for both biomarker and any model of PSA PFS or Radiological/Clinical PFS.

Even if fewer than 20 patients have information available, this is the first look at these measures. Therefore, the descriptive information gathered on biological markers and outcomes, as well as the feasibility of collecting such information in future trials will be valuable.

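### Two cells of Table 5 are wrong: at a 55% TOX rate the probability of enrolling at least 20 patients is 0.37, not 0.47, and at 50% the lower quartile of sample size is 9, not 11

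*Combined protocol and SAP*

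**What the plan says.** Section 11.2.4 gives the TOX probability a beta(0.8, 1.2) prior and stops the trial once "there is more than a 90% chance that the extreme toxicity rate is more than 40" per cent. On timing, "continual monitoring after the 6th patient is planned". Table 4 turns the rule into limits: for each TOX count, "Stop if there are this many or fewer patients treated". The upper end is fixed: "If the trial enrolls 27 patients, the trial will stop there regardless of the number of patients with TOX".

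Table 5 is titled "Operating Characteristics for the Toxicity Monitoring Rule assuming all 27 patients are enrolled". Its column "Probability of Enrolling ≥ 20 Patients" reads 0.98, 0.95, 0.89, 0.80, 0.67, 0.53 and 0.47 for true TOX rates of 25% to 55% in steps of 5 points. Its last column gives the median and quartiles of sample size: 20 (11, 27) at 50% and 13 (7, 26) at 55%.

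Section 11.3 says that 20 evaluable patients suffice to establish safety "as shown in Table 5 above while providing sufficient numbers for the secondary endpoints".

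**The concern.** The 55% row is out of line with the rows above it. The probability of reaching 20 patients, less the probability of reaching 27 (one minus the early-stopping probability), is the probability of stopping at 20 to 26 patients. From the printed figures:

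- 45%: 0.67 − (1 − 0.41) = 0.08
- 50%: 0.53 − (1 − 0.59) = 0.12
- 55%: 0.47 − (1 − 0.75) = 0.22

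The jump from 0.12 to 0.22 is abrupt for a rule that, at 55%, stops most trials well before 20 patients (printed median 13).

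Safety is the primary objective, and Table 5 is the plan's only quantitative account of how the safety rule performs. The 0.47 makes a roughly one-in-three chance of reaching 20 patients look nearly even. The lower quartile of 11 makes the earliest stops at a 50% rate look later than they are.

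**Working it through.** **Inputs, all from Section 11.2.4.** Prior beta(0.8, 1.2); stop if Pr(rate > 0.40 | data) > 0.90; looks after every patient from the 6th to the 26th; maximum 27, with no toxicity stop counted at 27; no earlier stop for evaluability, as the title of Table 5 assumes.

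**Step 1: the limits.** With x TOX events in n patients the posterior is beta(0.8 + x, 1.2 + n − x). The largest n at which its upper tail beyond 0.40 exceeds 0.90 is, for x = 5 to 14: 7, 9, 11, 13, 15, 17, 20, 22, 24, 26. These are the Table 4 limits.

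**Step 2: the whole table.** Let f(n, y) be the probability of having y TOX events after n patients without having stopped. For true rate p,

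f(n, y) = (1 − p) f(n − 1, y) + p f(n − 1, y − 1),

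and at each look the mass at or beyond the limit is removed and counted as stopping at n. The result is exact, with no simulation error.

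| TOX rate | Stop early | P(N ≥ 20): exact / printed | Mean N | Mean TOX | Median (quartiles): exact / printed |
|---|---|---|---|---|---|
| 25% | 0.023 | 0.979 / 0.98 | 26.6 | 6.65 | 27 (27, 27) / same |
| 30% | 0.059 | 0.947 / 0.95 | 26.0 | 7.81 | 27 (27, 27) / same |
| 35% | 0.131 | 0.890 / 0.89 | 25.0 | 8.74 | 27 (27, 27) / same |
| 40% | 0.248 | 0.799 / 0.80 | 23.3 | 9.32 | 27 (27, 27) / same |
| 45% | 0.407 | 0.675 / 0.67 | 21.0 | 9.46 | 27 (13, 27) / same |
| 50% | 0.586 | 0.525 / 0.53 | 18.3 | 9.16 | **20 (9, 27) / 20 (11, 27)** |
| 55% | 0.753 | **0.369 / 0.47** | 15.5 | 8.50 | 13 (7, 26) / same |

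Table 5 holds 7 rows of 7 figures, 49 in all. Every early-stopping probability, mean sample size and mean TOX count agrees to rounding, as do all other entries except the two in bold: 47 of 49.

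**Step 3: the 55% cell.** The exact stopping probabilities at 20, 22, 24 and 26 patients are 0.0480, 0.0302, 0.0238 and 0.0199, which sum to 0.122. Adding 0.247 for reaching 27 gives 0.369. A simulation of 400,000 trials gave 0.368.

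**Step 4: the 50% quartile, by hand.** At p = 0.5:

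- Stop at 6 (5 or 6 TOX in 6): (6 + 1)/64 = 7/64 = 0.109.
- Stop at 7 (4 in 6, then TOX): 15/64 × 1/2 = 15/128 = 0.117.
- No stop is possible at 8.
- Stop at 9: 4 in 7 without having stopped has probability (15 + 20)/128 = 35/128; two further TOX events give 35/512 = 0.068.

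So P(N ≤ 8) = 0.227 and P(N ≤ 9) = (56 + 60 + 35)/512 = 151/512 = 0.295. The 25th percentile is 9; a value of 11 would need P(N ≤ 9) below 0.25.

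**Step 5: other readings.** Looks from the first patient give 0.31 at 55%. A first look at patient 5, 7, 8 or 9, or an added look at 27, gives at most 0.38 at 55% and at most 9 for the 50% quartile. Reading the column as more than 20 patients gives 0.32 at 55%. Looks every 2 patients from the 6th give 0.49 at 55% and a 50% quartile of 12, which is nearer. That schedule also gives a mean of 17.2 and a median of 18 at 55%, against the printed and otherwise reproduced 15.5 and 13.

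**The case against.** The arithmetic is not open to dispute; the case on the other side is about consequence.

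First, both cells describe true rates above the 40% maximum, where early stopping is what one wants. The early-stopping probabilities, means and medians in those rows are right, and so is every row at or below 40%. No stopping decision changes. This stands, and it limits the severity.

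Second, the wording of Section 11.3 ties Table 5 most directly to safety; the secondary endpoints get their own Cox-model power statement at 20 patients, and the section accepts that fewer may be available. This stands in part. The same sentence also claims enough patients for those endpoints, and the probability of reaching 20 is the Table 5 column that bears on that claim.

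Third, a printed median of 13 already tells the reader that fewer than half of trials at 55% reach 20 patients. That is true, but it does not make 0.47 correct.

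Fourth, Section 11.2.4 warns that the percentiles may be slightly too high. That caveat concerns stopping for evaluability at 20 patients or later, so it cannot move a lower quartile of 9, and Table 5 assumes that all 27 are enrolled.

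Fifth, Section 11.2.4 also speaks of monthly monitoring and of reports in steps of 2 subjects, so two corrected cells would still describe patient-by-patient looks. This is fair, but it is a separate matter that affects the whole table.

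**Conclusion.** The point holds. At a 55% TOX rate the probability of enrolling at least 20 patients is 0.369 against the printed 0.47: an absolute error of 0.10, and 0.10/0.369 = 27% in relative terms. At 50% the lower quartile of sample size is 9 against the printed 11. Both results assume the rule as Table 5 states it: looks after each patient from the 6th, and all 27 enrolled unless toxicity stops the trial. That setup is confirmed by the 47 figures it reproduces. The error is confined to these two cells. It should be corrected because Section 11.3 cites the table to justify the sample size, but it does not affect the safety of the rule. Why the two figures are wrong cannot be determined from the document.

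**What to change.** In Table 5, change the 55% entry for enrolling at least 20 patients to 0.37, and the 50% entry for median and quartiles to 20 (9, 27). The cost is two numbers in one table; the prior, the stopping rule, Table 4 and the sample size stay as they are. Alternatively, if Table 5 is re-simulated under the review schedule that will actually be used, replace these cells along with the others and state that schedule in the table title.

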# 11.3 Determination of sample size

The selection of 20 evaluable patients was intended as a pilot sample size with sufficient numbers to establish safety in this population as shown in Table 5 above while providing sufficient numbers for the secondary endpoints. This will allow investigation of a few marker endpoints and establish safety and feasibility of measuring the markers of interest while being able to accrue within 6 months. No formal hypotheses are planned. These patients will form the basis of designing a hypothesis-driven study in the future. However, we can make a statement about what might be detected in secondary endpoints at this sample size. The association between CD3 change and PSA PFS will be explored with a Cox model with CD3 as a continuous measure. Assuming that

75% (80%) of patients will progress by the end of the study, 20 patients will have 80% power to detect a regression coefficient of 0.72 (0.70) at a 2-sided 5% significance level, assuming the change in CD3 has a standard deviation of 1. The regression coefficient of 0.72 (0.70) is equivalent to a hazard ratio of 2.1 (2.0) or a doubling of risk per unit increase in CD3 (Calculations performed in NCSS-PASS 2005). This would hold true for both biomarker and any model of PSA PFS or Radiological/Clinical PFS.

Even if fewer than 20 patients have information available, this is the first look at these measures. Therefore, the descriptive information gathered on biological markers and outcomes, as well as the feasibility of collecting such information in future trials will be valuable.

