#### 2.0 STUDY OBJECTIVE

## 2.1 Primary objective(s)

• To evaluate the safety and tolerability of durvalumab plus tremelimumab in patients with metastatic castration-resistant prostate cancer.

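### Section 11.3 says the sample can establish safety by reference to Table 5, but Table 5 only describes a stop for excess toxicity, and no final TOX rate is planned

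*Combined protocol and SAP*

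**What the plan says.** The only primary objective, in Section 2.1, is "To evaluate the safety and tolerability of durvalumab plus tremelimumab in patients with metastatic castration-resistant prostate cancer".

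Section 11.2.1 defines TOX, the key safety quantity, only for use in the interim monitoring. The qualifying event is "any grade 3 or higher adverse event that is possibly, probably, or definitely related to any therapy received on this protocol", provided that it falls in the first 8 weeks. A steroid-treatable event counts only if it has not improved to grade 1 or better after 2 weeks of steroids. For the final analysis the same section says: "At the end of the trial, all adverse events will be tabulated by their CTCAE v4.03 name, counted once at the worst grade", together with attribution. Presentation by cycle is optional.

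Section 11.2.4 gives the TOX rate a beta(0.8, 1.2) prior and stops the trial if the posterior probability that the rate exceeds 40% is above 0.90. It calls 40% "a constant rate that is the maximum acceptable for TOX". Table 4 lists the boundaries and Table 5 the operating characteristics, on the assumption that all 27 patients enrol. Enrolment ends at 27 whatever the TOX count. It may end anywhere from 20 to 27 once 20 patients are evaluable.

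Section 11.3 then defends 20 evaluable patients as "sufficient numbers to establish safety in this population as shown in Table 5 above". The same paragraph calls the study a pilot and plans no formal hypotheses.

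**The concern.** A stopping table answers one question: how often does the trial halt if the true rate is some given value? Establishing safety needs an answer to another: what do the final data say about the rate, and how precisely? Section 11.3 cites the first as evidence for the second. The rule acts only on strong evidence of excess, so its silence is weak evidence of acceptability.

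The gap would matter less if the final analysis reported the rate, but TOX is defined for interim use only. It is a composite per patient, with a time window, an attribution condition and a steroid exception. A table of events by term does not show how many patients met it. The one safety quantity with a stated maximum would then have no planned final estimate, and the later hypothesis-driven study that Section 11.3 has in view would lack a pre-specified figure to build on.

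**Working it through.** **Inputs.** The prior, the 0.90 threshold, the 40% limit and the Table 4 boundaries (5/7, 6/9, 7/11, 8/13, 9/15, 10/17, 11/20, 12/22, 13/24, 14/26) come from Section 11.2.4. Looks are taken after each patient from the 6th to the 26th, with none at 27.

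**1. Reproduce Table 4.** After x TOX in n patients the posterior is Beta(0.8 + x, 1.2 + n − x). For each x, take the largest n with Pr(rate > 0.40) > 0.90. All ten boundaries reproduce. For example, 11/20 gives 0.901 and 11/21 gives 0.861.

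**2. Reproduce Table 5 and take the complement.** An exact binomial recursion over the Table 4 boundaries gives:

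| True TOX rate | P(stop early), Table 5 | P(stop early), recomputed | P(complete) = 1 − Table 5 |
|---|---|---|---|
| 25% | 0.02 | 0.023 | 0.98 |
| 30% | 0.06 | 0.059 | 0.94 |
| 35% | 0.13 | 0.131 | 0.87 |
| 40% | 0.25 | 0.248 | 0.75 |
| 45% | 0.41 | 0.407 | 0.59 |
| 50% | 0.59 | 0.586 | 0.41 |
| 55% | 0.75 | 0.753 | 0.25 |

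The stopping column agrees throughout. Two other cells do not reproduce: the probability of enrolling at least 20 at 55% (0.37 against 0.47 printed) and the 25th percentile of sample size at 50% (9 against 11 printed). Neither bears on this point.

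**3. Use 20 patients instead of 27.** Section 11.3 defends 20 evaluable patients. If the first 20 treated are all evaluable and the trial ends there, the probability of not having stopped is 0.78 at a true 40% and 0.48 at 50% with a look at the 20th patient. Without that look it is 0.80 and 0.53. Completion is then more likely than at 27. Section 11.2.4 itself says that Table 5 overstates early stopping in such cases.

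**4. What a completed trial can look like.** At a true rate of 45%, 34% of all trials complete at 27 with an observed TOX proportion above 40% (11 or more of 27).

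The highest count compatible with completion is 14/27 = 51.9%: 13/26 does not stop, and there is no look at 27. Its exact 95% CI is 31.9% to 71.3%, and the posterior Beta(14.8, 14.2) gives Pr(rate > 0.40) = 0.883. This is an extreme, with probability 1.5% at a true 40%, 2.5% at 45% and 3.2% at 50%. It assumes that every TOX is known at each look.

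**5. Precision of a final estimate (Clopper-Pearson 95%).**

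| TOX / treated | Proportion | Exact 95% CI | Pr(rate > 0.40), plan's model |
|---|---|---|---|
| 5/20 | 25% | 8.7% to 49.1% | 0.081 |
| 8/20 | 40% | 19.1% to 63.9% | 0.488 |
| 7/27 | 26% | 11.1% to 46.3% | 0.063 |
| 11/27 | 41% | 22.4% to 61.2% | 0.521 |

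The sample can estimate the rate, with wide limits. All four results are compatible with completing the trial, and they carry very different messages about the 40% limit.

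**The case against.** The completion probabilities are not hidden: they are one minus a printed column, and Section 11.2.4 says openly that enrolment ends at 27 whatever the TOX count. Tolerating some completion above 40% is a legitimate design choice. The sentence in Section 11.3 also speaks of a pilot, formal hypotheses are disclaimed, and Section 2.1 says evaluate. No section states that failing to cross the boundary means TOX is at most 40%. The IND Office also reviews toxicity after the first 6 patients have had 2 cycles and then every 2 patients, so a high rate would not go unseen. Running Table 4 requires each patient's TOX status, so the count will exist.

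All of that stands, and it limits the point to wording and one missing summary. It does not rescue the citation of Table 5, and a count that exists but is not planned for report leaves the population and interval to be chosen afterwards.

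Three stronger readings are tempting, and the documents support none of them.

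- **That the trial is likely to finish with about 52% TOX.** It can, but with probability of about 3% or less at any rate in Table 5.
- **That the design fails unless TOX is at most 3/20 or 5/27.** Those are the largest counts whose exact two-sided 95% upper limit is below 40%, but the plan sets no such criterion. Its own model already puts Pr(rate > 0.40) at 0.06 for 7/27.
- **That the monitoring rule is wrong or the study too small.** The boundaries and stopping probabilities reproduce, and a pilot without hypotheses has no safety power to fall short of.

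**Conclusion.** The point holds as a defect of justification and reporting. Table 5 shows how often the rule stops for excess toxicity. It does not show that 20 patients establish safety. At the plan's own maximum acceptable rate the trial completes three times in four, and at a true 50% about two times in five. The final analysis then gives no TOX proportion or interval for the primary objective.

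The 27-patient figures assume a look after every patient from the 6th to the 26th with TOX status known at once. With looks every 2 patients, completion is somewhat more likely: 0.79 at 40% (1 − 0.206) and 0.45 at 50% (1 − 0.549). The conclusion does not depend on the 14/27 extreme. The correction should be made, but it alters no boundary, sample size or conduct.

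**What to change.** 1. **Section 11.3.** Replace the claim about establishing safety. Say that the rule in Section 11.2.4 monitors for excess toxicity and that the sample estimates the TOX rate, and state the precision, for example 5/20 = 25% with exact 95% CI 9% to 49%. Note that Table 5 is computed for 27 patients.
2. **Section 11.2.1.** Add the final TOX proportion in all patients who received at least one dose, with an exact 95% CI. A posterior summary from the beta(0.8, 1.2) model is optional.
3. **Either section.** State that completing without crossing the boundary is not a conclusion that the TOX rate is at most 40%.

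The cost is a few lines of analysis on data that the monitoring already requires, and a less favourable sample-size statement.
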